7.2.2 Secondary Efficacy endpoint

The secondary efficacy endpoint is the group mean HSM score (in quiet) of 40% or more at twelve months after the first fitting.

Subsidiary efficacy endpoints include:

- The mean monosyllabic word recognition score with the EAS system in quiet at 6, 12 months, 2, 3, 4 and 5 years after the first fitting
- The mean sentence recognition score with the EAS system in quiet at 6, 12 months, 2, 3, 4 and 5 years after the first fitting
- The mean sentence recognition score with the EAS system in noise at 6, 12 months, 2, 3, 4 and 5 years after the first fitting.

Regarding the sentence recognition score, either HSM sentence test or the OISa recognition score were collected during the clinical routine. The center initially collected the HSM sentence test routinely and then switched to the OISa recognition score. Therefore, throughout follow-up the speech test used to evaluate performance may have changed. Regarding the secondary objective and associated endpoint, the HSM sentence test will be used.

7.2.3 Safety Endpoint

This investigation focuses only on performance aspects. This retrospective data analysis is conducted for PMCF purpose as required following clinical evaluation of the device. The need for additional performance data specific to EAS user was identified.

7.3 Study Procedures

7.3.1 Description of all the clinical investigation related procedures for the subjects

As a retrospective analysis, this study does not include any investigational procedure outside of the clinical routine for the included patients.

7.3.2 Measurements procedures

The original publications describing the tests carried out are presented in the appendices (*Hahlbrock, 1953, Hochmair-Desoyer et al., 1997 and Wagener et al. 1999*).

Publications demonstrating the accuracy of the Freiburger Monosyllabic Word, Hochmair-Schulz-Moser and Oldenburger Sentence tests for evaluating speech understanding applied to the German language are listed in the bibliography section. Please note that these publications are in German.

- Freiburger Monosyllabic Word Test

The Freiburger Monosyllabic Word Test was conducted with a clinical audiometer. The signal was presented at 65dB from a loudspeaker in front of the subject. The loudspeaker presenting the material was placed one meter in front of the CI recipient. The score was obtained as the percentage of words correctly understood.

Conditions: at baseline the monosyllabic word test was conducted in free field on the ear to be implanted. The patient used the hearing aid setting with which he/she obtained best results. The score obtained was the baseline monosyllabic word score. With the CI system the monosyllabic word test was measured in free field using the processor in its normally used setting.

- Hochmair-Schulz-Moser Sentence Test

The Hochmair-Schulz-Moser (HSM) Sentence Test was conducted with a clinical audiometer. The signal was presented at 65dB from a loudspeaker in front of the subject. The loudspeaker presenting the material was placed one meter in front of the CI recipient. The score was obtained as the percentage of words correctly understood.

For speech intelligibility in noise a speech-shaped noise was presented additionally at 55dB SPL (SNR of +10dB).

Conditions: at baseline the HSM test was conducted in free field on the ear to be implanted. The patient used the hearing aid setting with which he/she obtained best results. With the CI system the HSM test was measured in free field using the processor in its normally used setting.

- Oldenburger Sentence Test (OISa)

The Oldenburger Sentence Test was performed in an adaptive way using a clinical audiometer. Both, signal and noise, were presented from the loudspeaker in front of the subject. The noise was presented at 65dB in a continuous way. The signal was varied to obtain the signal-to-noise ratio at which the patient correctly understood 50% of the words. This is called Speech Reception Threshold (SRT) measured in dB.

Conditions: at baseline the OIsa was conducted in free field on the ear to be implanted. The patient used the hearing aid setting with which he/she obtained best results. The SRT obtained in this condition was the baseline SRT. With the CI system the OIsa was measured in free field using the processor in its normally used setting.

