14.3 Data Management Procedures / Case Report Forms

As this is a retrospective observational study, the data were collected from the center database (MHH in Hanover, Germany), therefore, there are no Case Report Forms (CRF). Data source documents are the medical files of the patients, as filled in the center database.

The MHH will provide anonymized clinical data in the form of a spreadsheet including speech performance tests data and demographic data.

Details of the data collected are presented in the following list.

- Consent
- Demographics:
 - Native language
 - Age at implantation
 - Gender
 - Etiology
 - Implant (type, date, side)
 - Hearing aid (start right, end right, start left, end left)
 - Hearing impairment (right, left)
- Speech performance:
 - Freiburger Monosyllables (quiet) at 6 months, 1 year, 2 years, 3 years, 4 years and 5 years after first fitting with the acoustic earhook as available
 - HSM and/or Olsa (quiet) at 6 months, 1 year, 2 years, 3 years, 4 years and 5 years after first fitting with the acoustic earhook as available
 - HSM in noise (55dB SPL (SNR of +10dB)) and/or Olsa in noise (50% SRT with a 65dB noise signal) at 6 months, 1 year, 2 years, 3 years, 4 years and 5 years after first fitting with the acoustic earhook as available

14.4 Procedures used for data review, database cleaning, and issuing and resolving data queries

Retrospective anonymized data exported from the clinical patient database will be made available to AB in a spreadsheet format. The investigator ensures data integrity as providing anonymized data does not allow for data monitoring on behalf of AB.

14.5 Procedures for verification, validation and securing of electronic clinical data system (if applicable)

This section does not apply, as no data collection form (CRF) is used.

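### The plan has no rule for OlSa tests that never reach 50% correct, so the mean in-noise result at each visit may leave out the weakest tested patients and its trend may mislead

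*Combined protocol and SAP*

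**What the plan says.** Section 7.3.2 sets out the OlSa procedure. On the masker: "The noise was presented at 65dB in a continuous way". On the target: "The signal was varied to obtain the signal-to-noise ratio at which the patient correctly understood 50% of the words". On the scale: "This is called Speech Reception Threshold (SRT) measured in dB".

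The third subsidiary endpoint in Section 7.2.2 is "The mean sentence recognition score with the EAS system in noise at 6, 12 months, 2, 3, 4 and 5 years after the first fitting". It does not distinguish the two sentence tests, although the same section says: "The center initially collected the HSM sentence test routinely and then switched to the OISa recognition score". The HSM result is a percentage and the OlSa result is a level in dB.

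Section 14.3 lists the OlSa SRT in noise among the items to be extracted at each visit, to the extent that it is available. Section 8.2.1 promises descriptive statistics and leaves parametric or nonparametric methods open. No section gives a code, cap, count or ranking for a test in which 50% was not reached, or a same-patient comparison between visits.

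**The concern.** An SRT exists only if the patient can get half the words right somewhere in the range of levels presented. Failure to reach that point is not a random gap, because it marks the poorest performers. If those tests sit in the spreadsheet as blanks, they look the same as visits at which the OlSa was never given, and a mean over the remaining values is selected on the outcome itself.

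Two things follow. At any one visit the mean SRT looks better than the tested group really is. Across visits, the set of measurable patients changes with performance: weak patients who improve enter with poor SRTs and pull the mean towards worse, and patients who deteriorate out of range pull it towards better. Section 6.2 names the evolution of in-noise scores as an objective, and Section 12.2 counts hearing in noise as part of the intended benefit, so the direction of this trend should be interpretable.

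**Working it through.** The plan states no OlSa figure, so there is nothing to reproduce. Every distribution, SD, slope and SRT value below is an assumption. From the documents come only the definition of the SRT, the expected 30 to 40 subjects (Section 7.1.1), the 65 dB presentation levels (Section 7.3.2) and the visit schedule.

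**1. When an SRT exists.** Let the proportion correct at SNR x be p(x) = q / (1 + exp(-k(x - m))), with q the best score attainable at the levels the OlSa can present. Setting p = 0.5 gives exp(-k(x - m)) = 2q - 1, so SRT = m - ln(2q - 1)/k. This has a solution only if q > 0.5, and it grows without bound as q falls towards 0.5.

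**2. How many patients might be affected.** Scores in quiet stand in for q. For a beta distribution with mean μ and SD σ, put c = μ(1 - μ)/σ² - 1 and take Beta(μc, (1 - μ)c). For example, μ = 0.40 and σ = 0.20 give c = 0.24/0.04 - 1 = 5, hence Beta(2, 3), and P(score < 50%) = 11/16 = 69%.

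| Assumed mean in quiet | SD 20 | SD 25 | SD 30 |
|---|---|---|---|
| 40% | 69% | 65% | 63% |
| 60% | 31% | 35% | 37% |
| 75% | 13% | 18% | 22% |
| 85% | 8% | 12% | 14% |

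The extremes correspond to about 2.5 of 30 patients and 27.5 of 40.

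**3. How the trend can reverse.** Let n₀ patients be measurable with mean SRT M. Each improves by d, and n₁ others become measurable with mean SRT S. The new mean is (n₀(M - d) + n₁S)/(n₀ + n₁). It is worse than M whenever S > M + n₀d/n₁.

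| n₀ | n₁ | M (dB) | d (dB) | S (dB) | New mean (dB) | Break-even S (dB) |
|---|---|---|---|---|---|---|
| 7 | 3 | 2.0 | 1.0 | 10 | (7×1 + 3×10)/10 = 3.7 | 4.3 |
| 20 | 5 | 2.0 | 0.5 | 10 | (20×1.5 + 5×10)/25 = 3.2 | 4.0 |
| 25 | 3 | 2.0 | 0.5 | 10 | (25×1.5 + 3×10)/28 = 2.41 | 6.2 |
| 30 | 1 | 0.0 | 0.5 | 8 | (30×(-0.5) + 1×8)/31 = -0.23 | 15.0 |

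In the first three rows the mean worsens although every patient improved. In the last it does not. Read backwards, the first row is a cohort in which all 10 deteriorate while the observed mean improves from 3.7 to 2.0 dB.

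**4. Simulation.** Cohorts of 35 were simulated 10,000 times in each of four settings. Ceilings q had mean 50%, 60% (twice) or 75% and SD 25 points. Midpoints m had mean 0 and SD 2 dB, k was 0.4 per dB, and there was no upper limit on level. Every ceiling rose by 5% or 10% of its distance to 100%. At the first visit 18-50% of patients had no SRT. The observed mean SRT worsened in 37-43% of runs, and its average change was only -0.01 to -0.06 dB.

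**5. If the center stored a limit value L instead.** At the first visit of the 10-patient example the mean would be (7×2 + 3L)/10 = 1.4 + 0.3L. It would then depend on the test's limit, moving 0.3 dB for each dB in L.

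**6. The ranked median on the same example.** Suppose the seven measurable patients all sit at their mean and 'not reached' ranks worst. The median of 10 is then +2 dB at the first visit and +1 dB at the second, and all 10 count as improved. The direction is right.

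**The case against.** Several stronger readings are tempting, and the documents do not support them.

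- *Poor performers are dropped.* No section says that an unreached 50% point is left blank. The center may have stored a limit value. The only documented reason for a missing OlSa result is the change of test, which is not described as depending on performance.
- *Anyone below 50% in quiet has no SRT.* The quiet tests use a fixed 65 dB signal. The OlSa holds the noise at 65 dB and varies the signal, so at positive SNRs the speech is louder than in the quiet tests. A patient below 50% at 65 dB in quiet may still reach 50%.
- *The plan itself expects most patients to fail.* The secondary criterion, "the group mean HSM score (in quiet) of 40% or more at twelve months after the first fitting", is a pass mark on a different test, not a forecast. The 63-69% applies only to a cohort whose mean sits at that mark.
- *The trend will be wrong even in a fixed set of patients.* If the set is those with an SRT at both visits, the mean cannot worsen when all of them improve (2.0 to 1.0 dB in the first example). What remains is that the result speaks for 7 of the 10.

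It is also fair that Section 8.2.1 already allows nonparametric methods and that little hangs on this endpoint. These objections limit certainty, size and reach. They do not remove the gap: the plan names a mean for an outcome that can be undefined for the weakest patients, and gives no rule for that case.

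**Conclusion.** The concern holds in conditional form. The OlSa SRT is undefined for a patient who cannot reach 50% at the highest level presented, and the plan averages whatever values are available without a rule for such tests. If they are blank, the mean SRT is biased in the device's favour and its trend can run opposite to what patients experience. If a limit value was stored, the mean depends on that limit. The share affected cannot be estimated from the documents. The 8-69% range rests on assumed beta distributions and on scores in quiet at 65 dB as a proxy, and the reversal is possible rather than certain. The reach is narrow: only the descriptive subsidiary in-noise trend is affected. The primary endpoint uses the Freiburger words, the secondary endpoint uses the HSM, and the pass/fail rule in Section 8.2.3 depends on the primary hypothesis alone.

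**What to change.** In Section 14.3, ask the center to code each OlSa visit as one of: SRT value; tested but 50% not reached (with any limit value stored); not tested; reason unknown. This has to be requested at extraction, because the sponsor cannot check source data (Section 14.1) and the spreadsheet is deleted once the report is final (Section 14.8).

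In Section 7.2.2, first separate OlSa SRT (dB) from HSM (%), since the present endpoint has no distinct OlSa mean to replace. Then, for the OlSa at each visit, report the number tested, the number and percentage of those reaching an SRT, and the median SRT with 'not reached' ranked worst, in place of a mean. Report within-patient change between visits as improved, unchanged or worse, using the same ranking.

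The cost is one extra column and a change of summary statistic, with no new testing. The limits should be stated: some old records may not show why a score is absent; patients never given the OlSa because failure was expected remain uncounted; and the median can be reported only as 'not reached' when more than half of those tested fail.

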7.3.3 Methods and timing for assessing, recording and analyzing variables

The data collected for this retrospective observational study were already collected by the expert center as part of the clinical routine management of patients. Analysis to be performed for this investigation is described in section 8.2.

7.3.4 Equipment to be used for assessing the clinical investigation variables

To obtain speech perception scores and in the Freiburger monosyllabic word test, the HSM sentence test and speech reception threshold in the Oldenburger sentence test, the clinics used a standard audiometer where the respective tests are implemented.

7.3.5 Description of those activities performed by Sponsor representatives

The anonymized data will be analyzed by the Sponsor and a report will be provided to the investigator. The Sponsor is responsible for any regulatory requirements, as applicable.

7.3.6 Any known or foreseeable factors that may compromise the outcome of the clinical investigation or the interpretation of results

The study carried out is a monocentric study, which may constitute a bias: the population may not reflect the overall population using the acoustic earhook. Additionally, only anonymized data will be provided to AB, preventing the possibility to verify source data. Therefore, no monitoring will be performed for this investigation.

7.3.7 Methods for addressing these factors in the clinical investigation

There are no methods for addressing the potential bias due to the study being monocentric within the clinical investigation, except performing additional clinical investigations in other centers.

In order to ensure the validity of the transmitted data, a contract will be drawn up between the centre and AB with the aim of defining roles and responsibilities. The center will be responsible for the verification of the validity of the data.

7.3.8 Specific subject's follow-up after termination of the study

Not applicable, this a retrospective observational study for which the data were already collected in the context of the clinical routine care.

7.4 Study Visits and Visit Windows

All data analyzed will be collected retrospectively from the clinical database, no dedicated visits are necessary for this protocol. The scheduled routine of patient care visits is presented in the **Error! Reference source not found..**

Table 9 : Schedule of clinical routine patient care visits at MHH

Procedures	Pre-Op	Surgery	First Fitting	Follow-up fitting (3 and 6 Mo)	Yearly Appointment (1 year, 2, 3, 4, 5... years)
Counselling, selection of implant manufacturer	X				
Pure tone audiometry	X		X	X	X
Implantation of cochlear implant		X			
Implant check		X	X	X	X
Imaging		X			
Rehabilitation training			X		
Medical check	X		X		X
Speech perception test	X		X	X	X
Finetuning of fitting			X	X	X

7.5 Withdrawal of Subjects

This section is not applicable to a retrospective data analysis. However, a subject's data may be withdrawn from the analysis if it is subsequently discovered that the inclusion of a subject does not comply with the selection criteria.

8.0 Statistics

8.1 Sample Size Justification

This analysis only includes retrospective clinical data. All data from subjects fulfilling the inclusion criteria will be included.

8.2 Statistical Design & Data Analysis

8.2.1 Analytical procedures

Data will be analyzed using descriptive statistics and further analyses might be performed using applicable parametric or nonparametric methods, depending on the number of available datasets.

The study plans to screen up to 50 patients. Among these 50 potential subjects, based on the estimation of patients who provided informed consent and who fulfill the inclusion criteria, the size of the included population is estimated to be around 30 to 40 subjects.

8.2.2 Primary efficacy hypothesis

The primary efficacy hypothesis is based on the total number of subjects n and score (percentage of words correctly understood) in the Freiburger Monosyllabic Word Test twelve months after the first fitting.

Thus, the primary efficacy hypothesis is:

$$\frac{\sum(\text{Word Score 12 months})}{N} > 30\%$$

With:

Word Score 12 months = % of words correctly recognized at 12 months after the first fitting

N = number of datasets

8.2.3 Secondary efficacy hypothesis

The second efficacy hypothesis is based on the total number of subjects n and score (percentage of words correctly understood) in the HSM sentence test in quiet and in noise one year post activation.

Thus, the secondary efficacy hypothesis is:

$$\frac{\sum(HSM \text{ Score } 12 \text{ months})}{N} > 40\%$$

With:

HSM Score 12 months = % of correct sentence recognized at 12 months in quiet and in noise after the first fitting

N = number of datasets

- **Pass/fail criteria to be applied to the results of the clinical investigation**

The primary efficacy hypothesis needs to be fulfilled in order to consider this investigation successful.

- **Procedure for reporting any deviation(s) from the original statistical plan**

In case of a deviation from the statistical plan, the final report will highlight and justify the deviations.

- **Minimum and maximum number of subjects to be included for each center in multicenter clinical investigations**

This section is not applicable. The study is a monocentric study.

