1.0 Synopsis

Study Title	Retrospective analysis of long-term speech performance in cochlear implant recipients using electro-acoustic stimulation
Sponsor	Advanced Bionics AG
Investigational Device	Naída CI M and Naída CI Q and associated acoustic earhooks
Study Design	A monocentric observational post-market clinical follow-up study (PMCF) based on a retrospective data analysis of anonymized clinical data
Study Population	All subjects fulfilling inclusion and exclusion criteria and registered in clinical patient database at the time of the extraction of the data
Inclusion Criteria	Being implanted with Ultra or Ultra 3D SlimJ Being a user of the "acoustic earhook" system Having provided informed consent regarding use of his/her data for research
Exclusion Criteria	N/A
Primary Study/Efficacy Objective	Mean monosyllabic word recognition score with the EAS system in quiet at twelve months after first fitting of 30% or better
Primary Study/Efficacy Endpoint	Group average on the Freiburger Monosyllabic Word Test (in quiet) of 30% or more at twelve-month after first fitting
Secondary Study/Efficacy Objective	Mean sentence recognition score with the EAS system in quiet at twelve months after first fitting of 40% or better
Secondary Study/Efficacy Endpoint	Group average in the HSM sentence test (in quiet) of 40% or more at twelve-month after first fitting
Safety Objective	N/A
PMCF Objective (if required)	Collection of additional clinical data on acoustic earhook performance
Study Schedule & Duration	Estimated time for data collection, analysis and writing of the report: 3 months

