6.2 Secondary Efficacy Objective

The secondary efficacy objective is to demonstrate that the group mean sentence recognition score with the EAS system in quiet at twelve months after first fitting is 40% or better.

Subsidiary objectives include:

- Observation of the evolution of the mean monosyllabic word recognition score with the EAS system in quiet at 6, 12 months, 2, 3, 4 and 5 years after first fitting and more if available
- Observation of the evolution of the mean sentence recognition score with the EAS system in quiet at 6, 12 months, 2, 3, 4 and 5 years after first fitting and more if available
- Observation of the evolution of the mean sentence recognition score with the EAS system in noise at 6, 12 months, 2, 3, 4 and 5 years after first fitting and more if available.

There are no safety objectives for this clinical investigation. Safety events will not be collected retrospectively for the included subjects.

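### The 40% secondary rule in Section 8.2.3 takes in HSM scores from both quiet and noise, while the stated secondary endpoint is HSM in quiet only

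*Combined protocol and SAP*

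**What the plan says.** Three places define the secondary target, and all restrict it to quiet:

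- Synopsis: "Group average in the HSM sentence test (in quiet) of 40% or more at twelve-month after first fitting".
- Section 6.2: the aim is to show that "the group mean sentence recognition score with the EAS system in quiet at twelve months after first fitting is 40% or better".
- Section 7.2.2: "The secondary efficacy endpoint is the group mean HSM score (in quiet) of 40% or more at twelve months after the first fitting".

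Section 7.2.2 then lists a subsidiary endpoint, "The mean sentence recognition score with the EAS system in noise", at several follow-up times and with no threshold.

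Section 8.2.3 is the only place that writes the secondary endpoint as a formula: a sum of 12-month HSM scores divided by N, required to exceed 40%. It defines the summed variable as "HSM Score 12 months = % of correct sentence recognized at 12 months in quiet and in noise after the first fitting". Its opening sentence also names both listening conditions, so noise appears twice in the section.

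On scoring, Section 7.3.2 says of the HSM test: "The score was obtained as the percentage of words correctly understood". The opening sentence of 8.2.3 also speaks of words, but the definition under the formula speaks of sentences.

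The closing part of 8.2.3 makes success of the investigation depend on the primary hypothesis only.

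**The concern.** A decision rule should measure the endpoint it serves. Here the endpoint is a mean in one listening condition, and the rule brings in a second, separately measured condition: speech-shaped noise at a signal-to-noise ratio of +10 dB (7.3.2). The 40% threshold matches the adult benefit claim in 12.2, which is also for sentences in quiet. The plan gives no basis for applying 40% to noise scores or to a mixture.

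At stake is the pass or fail result of the plan's only secondary hypothesis. An analyst following 8.2.3 and one following 7.2.2 could report opposite results from the same spreadsheet. Because the data already exist, choosing between the two texts after extraction would be a post hoc choice.

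**Working it through.** The plan gives no HSM mean, standard deviation, alpha or power for this hypothesis, so there is no figure of its own to reproduce. The check compares texts and then illustrates the size.

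**1. The texts side by side**

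| Element | Synopsis, 6.2, 7.2.2 | 8.2.3 |
|---|---|---|
| Condition | quiet | quiet and noise (stated twice) |
| Threshold | 40% or more / or better | strictly above 40% |
| Scoring unit | not stated here; words in 7.3.2 | words in the opening sentence, sentences in the definition |
| In-noise score | subsidiary, no threshold (7.2.2) | inside the 40% rule |

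**2. Two possible readings of 8.2.3**

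- *Pooled:* quiet and noise scores go into one sum with one N. The result is a weighted mean of two conditions, not the quiet mean.
- *Separate:* the same rule is applied to each condition. This adds a 40% criterion in noise that 7.2.2 does not contain.

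Neither reading reproduces the endpoint in 7.2.2, so the conflict does not depend on which was meant.

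**3. Size under pooling (assumed means)**

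Let q be the quiet mean, z the noise mean and w the share of quiet scores. Pooled mean = w·q + (1 − w)·z.

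With w = 0.5 and q = 50%:

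- z = 10%: 25 + 5 = 30%
- z = 20%: 25 + 10 = 35%
- z = 30%: 25 + 15 = 40%

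The quiet endpoint is met by 10 points in each case, yet all three fail a rule that requires more than 40%. The third fails only because the inequality is strict.

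The quiet mean that brings the pooled mean to exactly 40% is q = (40 − (1 − w)·z)/w:

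| w | z = 10% | z = 20% | z = 30% |
|---|---|---|---|
| 0.5 | 70.0% | 60.0% | 50.0% |
| 0.75 | 50.0% | 46.7% | 43.3% |

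So the effective hurdle in quiet ranges from 43.3% to 70% over these assumptions, against the stated 40%. The plan does not fix w. Section 7.2.2 says the center moved from HSM to OlSa over time, and 14.3 supplies scores as available, so w would depend on which records exist.

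**4. Size under separate tests**

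If both conditions must exceed 40%, the same assumed means (quiet 50%, noise 10 to 30%) fail on the noise part while the quiet endpoint is met.

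**The case against.** The strongest reply is that the intended endpoint is not in doubt. Three places say quiet, 7.2.2 keeps noise apart, and 14.3 requests quiet and noise scores as separate items, so the quiet mean can be computed directly. Study success does not depend on this rule. All of that stands, and it sets the severity. It does not remove the conflict, because 8.2.3 is the only formula and it names noise twice.

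A reader might infer several stronger points that the documents do not support:

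- *That the plan definitely pools the conditions.* It never says so. Separate tests are also possible, and the pooling arithmetic applies only to the first reading.
- *That the rule could as easily give a false pass.* Adding a quiet and a noise percentage per subject and dividing by subjects would allow it, but that puts a 0 to 200% scale against a 40% threshold, which is not a plausible reading. Under ordinary pooling, a false pass needs noise scores averaging above 40% while quiet scores average below 40%. The documents give no reason to expect that.
- *That whole-sentence scoring is a rival measure.* Section 7.3.2 and the opening sentence of 8.2.3 both say words, and nothing indicates that whole-sentence scores exist in the database, so the definition reads as loose wording. No conversion can be taken from the documents: if the sentence score is the word score raised to an assumed effective number of independent words, a 40% word score becomes 25.3% with 1.5 such words and 1.0% with 5.
- *That the unclear N is caused by counting quiet and noise twice.* The same switch between subjects and datasets appears in 8.2.2, where there is only one condition, and 5.7 notes that bilateral patients have two devices. A dataset may simply be an ear.
- *That 12.2 sets 40% in quiet for everyone.* That figure is for adults. For children above 4 years it gives 30% for words or sentences, and children are not excluded.

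**Conclusion.** The contradiction is real and rests on the text alone: the 40% rule in 8.2.3 covers quiet and noise, while the endpoint it should test covers quiet only. With assumed means, pooling raises the quiet score needed to somewhere between 43.3% and 70%, and a quiet mean of 50% can be reported as a failure. Those figures illustrate direction and scale; they are not predictions.

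The effect is confined to the secondary hypothesis. A reader might infer that the study's overall conclusion is at risk, but 8.2.3 ties success to the primary hypothesis alone. This is therefore a should-fix. Two smaller conflicts in the same section belong with it: sentences against words as the scoring unit, and strictly above 40% against 40% or more.

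**What to change.** Amend 8.2.3 before the sponsor analyses the data:

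1. Define the variable as the HSM score in quiet, percentage of words correct, at 12 months after first fitting.
2. Remove the noise condition from both the opening sentence and the definition under the formula.
3. Change the inequality to 40% or more, matching the synopsis, 6.2 and 7.2.2.
4. Use one quiet score per analysis unit, and state whether that unit is the subject or the implanted ear, consistently with 8.2.2.
5. Report HSM in noise only as the existing subsidiary endpoint, without a threshold.

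The cost is wording, through the formal amendment that 16.1 requires, and no new data are needed. Item 4 is a real decision, because it settles how bilateral users count in the primary and the secondary mean.

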6.0 Objectives

6.1 Primary Efficacy Objective

The primary efficacy objective is to demonstrate that the group mean monosyllabic word recognition score with the EAS system in quiet at twelve months after first fitting is 30% or better. This efficacy outcome has been defined in accordance with the State-Of-The-Art (SOTA) performed by AB, and claimed clinical benefits for the HiRes Bionic Ear System from AB.

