7.2 Study Endpoints

7.2.1 Primary Efficacy endpoint

The primary efficacy endpoint is the group mean Freiburger Monosyllabic Word score (in quiet) of 30% or more at twelve months after the first fitting.

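### Success is declared on the observed mean alone, with no confidence limit or test tied to the decision, although the stated aim is to demonstrate a group mean of 30% or better

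*Combined protocol and SAP*

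**What the plan says.** The primary objective in Section 6.1 is confirmatory in wording: "The primary efficacy objective is to demonstrate that the group mean monosyllabic word recognition score with the EAS system in quiet at twelve months" is at or above the threshold. Section 7.2.1 gives the endpoint as "the group mean Freiburger Monosyllabic Word score (in quiet) of 30% or more at twelve months after the first fitting". Section 8.2.2 introduces the hypothesis with "The primary efficacy hypothesis is based on the total number of subjects n and score" and then writes it as the sum of the 12-month word scores over N, strictly greater than 30%. That is a statement about the sample average, not about a population mean.

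The pass/fail text under Section 8.2.3 then says: "The primary efficacy hypothesis needs to be fulfilled in order to consider this investigation successful". It names no other criterion. On inference, Section 8.2.1 plans descriptive statistics and adds that "further analyses might be performed using applicable parametric or nonparametric methods, depending on the number of available datasets". Section 8.1 gives no significance level, SD, power or target precision. The 30 to 40 subjects in Sections 7.1.1 and 8.2.1 are a feasibility estimate.

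The secondary hypothesis in Section 8.2.3 has the same form, with a sample mean above 40% on the HSM sentence test.

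**The concern.** A sample mean from a few dozen people varies. A rule that looks only at which side of 30% it falls on can declare success when the data are quite compatible with a true mean below the claimed benefit. That matters because Section 6.1 ties the threshold to the sponsor's claimed clinical benefit, Section 14.7 sends the result to the post-market follow-up report, and Section 7.1.4 wants the results to generalise beyond the patients studied. The optional analyses in Section 8.2.1 do not help: they are unspecified and nothing connects them to the success decision. A rank-based method, which the text allows, would not in general address the mean that the endpoint names.

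**Working it through.** There is no stated alpha, power or calculated sample size, so there is no figure of the plan's own to reproduce.

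**Inputs from the plan.** Threshold 30% (Section 8.2.2); N = 30 to 40 (Section 8.2.1).

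**Assumed.** Between-subject SD of 15, 20, 25 or 30 percentage points, because the plan gives none.

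**Step 1: chance of passing under the rule as written.** P(pass | true mean μ) = 1 − Φ((30 − μ) / (SD/√N)). As μ approaches 30 from below, this approaches 1 − Φ(0) = 50%, whatever SD and N are. For true means further below:

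| SD (assumed) | N | SD/√N | μ = 28% | μ = 27% | μ = 25% |
|---|---|---|---|---|---|
| 15 | 30 | 2.74 | 23.3% | 13.7% | 3.4% |
| 15 | 40 | 2.37 | 20.0% | 10.3% | 1.8% |
| 20 | 30 | 3.65 | 29.2% | 20.6% | 8.5% |
| 20 | 40 | 3.16 | 26.4% | 17.1% | 5.7% |
| 25 | 30 | 4.56 | 33.1% | 25.6% | 13.7% |
| 25 | 40 | 3.95 | 30.6% | 22.4% | 10.3% |
| 30 | 30 | 5.48 | 35.8% | 29.2% | 18.1% |
| 30 | 40 | 4.74 | 33.7% | 26.4% | 14.6% |

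**Step 2: is the normal approximation adequate?** Word scores are bounded and may be skewed. Simulating beta-distributed scores with mean 30% and the same SDs (200,000 runs per setting, N = 20, 30 and 40), both continuous and in 5% steps (assuming a 20-word list), gave pass probabilities of 48% to 51%. The approximation holds.

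**Step 3: how large must the observed mean be to exclude 30%?** Smallest passing mean = 30 + t(0.975, N − 1) × SD/√N.

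| SD (assumed) | N = 30 | N = 40 |
|---|---|---|
| 15 | 35.6% | 34.8% |
| 20 | 37.5% | 36.4% |
| 25 | 39.3% | 38.0% |
| 30 | 41.2% | 39.6% |

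An observed mean of 31% to 34% would thus be called a success in all eight settings while its interval still includes 30%. If only 20 subjects had a 12-month score, the range would be 37.0% (SD 15) to 44.0% (SD 30).

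**Step 4: effect of an interval rule.** Requiring the lower two-sided 95% t-limit to exceed 30% gives a nominal 2.5% pass rate at a true mean of 30%; the skewed simulations gave 1.5% to 1.9% for N = 30 to 40. From the noncentral t distribution, 80% power needs a true mean of 37.9% to 45.9% at N = 30 and 36.8% to 43.6% at N = 40, from SD 15 to SD 30. At a true mean of 45% power is 75% to 100%, and at 50% it is at least 94%.

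**The case against.** The strongest reply is that this is a retrospective, largely descriptive follow-up study of CE-marked devices. The synopsis gives its follow-up objective as collecting additional data, and no publication is planned (Section 17.0). The claimed benefit in Section 12.2 is itself a point value, so requiring a lower limit above 30% sets a stricter bar than the sponsor chose. This stands as far as the remedy goes: a purely descriptive report would be legitimate. It does not rescue the present text, which speaks of demonstrating, of a hypothesis and of success.

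A second reply is that the cohort is every eligible consenting user at one clinic, perhaps 30 to 40 of about 50, so little sampling error remains. If the target were only those 50 users and inclusion were like random sampling, the finite-population factor √((50 − N)/49) would be about 0.64 at N = 30 and 0.45 at N = 40. At SD 25 the 95% half-width would fall from 9.3 to about 6.0 points, or from 8.0 to about 3.6. But inclusion depends on consent and eligibility, not on random sampling, and Sections 5.5 and 7.1.4 aim at a wider population.

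Two stronger readings are tempting. A reader might infer that the rule has a 50% false-pass rate because a true mean of exactly 30% passes half the time. The synopsis and Sections 6.1 and 7.2.1 count exactly 30% as meeting the objective; only Section 8.2.2 uses a strict inequality. The 50% is therefore a limit approached from below, where the shortfall is small. A reader might also infer that the analysis method is to be picked once the scores are known. Section 8.2.1 ties the choice to how many datasets there are, not to their values, and those analyses do not feed the success decision.

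**Conclusion.** The concern holds in this form: the only criterion for success compares a sample mean with 30% and makes no allowance for sampling error, while the objective claims to demonstrate performance. This is more than missing detail, since following the rule exactly can yield a success claim on data compatible with a true mean below 30%.

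The limit of 50% just below the threshold does not depend on SD or N. The other sizes do: they rest on the assumed SD range and on 30 to 40 subjects contributing a 12-month score. Section 14.3 takes scores as available, so the number may be smaller and the imprecision greater. The plan states no expected mean, so nothing here implies that the system performs below 30%. If the true mean is well above it, the stricter rule would rarely change the conclusion.

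**What to change.** In Section 8.2.2 and the pass/fail text, state H0: mean ≤ 30% against H1: mean > 30%. Define success as the lower limit of the two-sided 95% t-interval for the mean 12-month Freiburger score exceeding 30%, with a bootstrap interval as sensitivity analysis. This replaces the open choice of method for these analyses.

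- **Unit of analysis.** Section 8.2.2 refers to subjects but defines N as datasets, and Section 5.7 notes that bilateral patients have two devices. Use one value per subject, or an interval clustered by subject if ears are the unit.
- **Secondary endpoint.** Use the same form with 40% for the HSM score in quiet, the condition named in Sections 6.2 and 7.2.2.
- **Threshold wording.** Align the synopsis and Sections 6.1 and 7.2.1 with the hypothesis, so that one inequality is used throughout.

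An equally valid alternative is to remove the language of demonstration and success and report each mean with its 95% confidence interval descriptively.

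Either route costs a short text amendment before the data are analysed, and no new data. The price of the first is that the observed mean must lie several points above 30% to claim success; the price of the second is the confirmatory claim itself.
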